9.7.2.3. Comparative safety analyses

The comparative analysis will estimate prevalence ratios and corresponding 95% CIs for each of the pregnancy or infant events comparing the PAXLOVID exposed pregnancy cohorts to the comparator pregnancy cohorts in the same exposure window (eg, Cohort 1 first trimester cohort versus Cohort 2 first trimester cohort; Cohort 1 first trimester cohort versus Cohort 3 first trimester cohort). Prevalence will be estimated for these outcomes because they develop during gestation but are only observable at birth; thus, only the prevalence at birth

can be calculated. Crude (unadjusted) and IPTW-adjusted prevalence ratios will be reported along with corresponding 95% CIs. The prevalence ratios will be estimated using robust Poisson regression models (Chen et al. 2018), with analysis of log-binomial models as sensitivity analysis.

Analyses based on claims-identified cases will be presented. However, the primary comparative analyses in the final report will only include outcomes that have been confirmed via medical record review or identified via published validated algorithms.

Planned analyses for each outcome are described in Table 4.

Comparative analyses will be performed overall and among subgroups according to presence of COVID-19 diagnoses occurring prior to exposure to cohort medications, as well as by hospitalization status at the time of COVID-19 diagnosis, sample size permitting.

Analyses will be conducted on MCMs collectively as a whole, with subgroup analyses by MCM subtype (for example, organ system affected) performed as sample size allows. The number of pregnancies with each outcome will serve to guide the analyses that are feasible.

Covariance between observations will be taken into account via robust standard errors if multiple pregnancies per woman are observed (Mansournia et al. 2021). Known confounders that are strongly associated with PAXLOVID use and the pregnancy or infant outcomes, or that remain imbalanced after weighting via IPTW, will also be included in the outcome regression models if standardized mean differences exceed >0.2 after IPTW (Austin 2009). Baseline covariates with an imbalance of 0.1-0.2 will be considered individually, taking into account their prevalence. Prior history of COVID-19 and the use of COVID-19 therapies during baseline and after cohort entry may be used for subgroup analysis. Other pregnancy characteristics (characteristics that are identified after baseline and that are therefore not incorporated into the propensity score models), such as COVID-19 severity, may also be considered for subgroups in secondary analysis.

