9. RESEARCH METHODS

9.1. Study design

This 5-year observational cohort study will use administrative healthcare claims data (the ORD) to assess PAXLOVID exposure and pregnancy and infant outcomes including SA, induced termination, stillbirth, livebirth, SGA, preterm birth, postnatal growth deficiency, and infant developmental delay and MCM. The primary outcome is MCM, which will be confirmed via medical record review. Pregnancies that begin (based on the ECD, equal to LMP + 14 days) between 01 March 2021 and 01 December 2025 will be identified. For the assessment of infant outcomes, pregnancies that begin on or before 01 April 2025 will be eligible for inclusion. Pregnancies that began in March 2021 are the earliest eligible PAXLOVID-exposed pregnancies in the US (ie, potentially exposed to PAXLOVID close to delivery in December 2021).

All qualifying pregnancies per woman will be included in the study and classified according to the COVID-19 treatments received during 2 relevant exposure windows:

- First trimester exposure window
- Full pregnancy exposure window

These 2 windows provide the flexibility to assess the timing of exposure during pregnancy, as the relevant etiologic period may be the first trimester for MCM whereas the full pregnancy may be the relevant exposure period for pregnancy or other infant outcomes. Given that COVID-19 treatment is typically administered shortly after COVID-19 diagnosis, these exposure windows will account for timing of COVID-19 during pregnancy as well.

[figure not shown]
Based on received COVID-19 treatments during each of 2 exposure windows (first trimester, pregnancy), the pregnancies will be classified into the following exposure cohorts (for a total of 6 cohorts):

- Cohort 1 (PAXLOVID cohorts): at least 1 dispensing of PAXLOVID within the relevant exposure window, and no evidence of comparator medications within the relevant exposure window
- Cohort 2 (Treated Comparator Only cohorts): no evidence in the study database of a dispensing of PAXLOVID, and dispensing or administration of at least 1 of the following treatments indicated for the treatment of mild-to-moderate COVID-19 within the relevant exposure window:
 - Remdesivir
 - Bebtelovimab
- Cohort 3 (Untreated Comparator cohorts): no evidence in the study database of a dispensing or administration of any COVID-19 treatments within the relevant exposure window

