9.3. Variables

9.3.1. Outcomes

The primary outcome is MCM. The secondary outcomes are SA, induced termination, stillbirth, livebirth, SGA, preterm birth, postnatal growth deficiency and

infant developmental. The study outcomes will be identified by ICD-10 diagnosis and procedure codes, CPT^{®2} procedure codes, and HCPCS procedure codes on claims. All outcomes will initially be identified via claims-based algorithms. Potential cases of MCM, induced termination, SGA, preterm birth, postnatal growth deficiency and infant developmental delay, and a sample of livebirths identified via claims-based algorithms will be adjudicated via medical records.

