9.3.1.3. Medical record confirmation of outcomes

Pregnancy and infant outcomes will be assessed using claims-based algorithms from the literature with adequate PPVs when available, otherwise confirmed via medical records. Andrade et al. observed a PPV of 83% for their ICD-10-based stillbirth algorithm, developed within an electronic health record database (Andrade et al. 2021). A recent Optum publication observed a PPV of 84.7% for the identification of SA (Chomistek et al. 2022). Optum proposes to use these published algorithms to identify SA and stillbirth.

Given that most pregnancies are expected to end in a livebirth, a random sample of 200 livebirths will be selected for medical record confirmation and validation of the livebirth identification algorithm, which relies on the presence of outcome-related ICD-10 codes. This conservative sample size is sufficient to exclude from the 95% confidence interval (CI) a PPV <80% if the true PPV is 85% (Schaeffer et al. 1990). Livebirths are identified via ICD-10 codes shown in ANNEX 2. ADDITIONAL INFORMATION.

Using medical records to confirm pregnancy and infant outcomes allows for a highly sensitive and specific outcome definition because medical records may be sought for all potential outcomes (high sensitivity) and each potential outcome is adjudicated (high specificity). The literature will be re-assessed following delivery of the final accrual report to identify alternative stillbirth and/or SA algorithms and algorithms for the remaining outcomes. If suitable algorithms are found, the proposed approach may be modified to use algorithms for additional outcomes (Tonelli et al. 2016).

For outcomes for which medical record confirmation is deemed necessary, a detailed review of the chronological listing of relevant claims (ie, claims profile) will be reviewed for each of the potential cases in order to:

- Determine if the claims listing for each potential case contains sufficient information to be included in the medical record procurement process; and
- Determine the medical site of treatment most likely to yield medical records with the necessary information to confirm case status.

Optum, with input from a clinician, will develop a medical record review form that will include clinical elements necessary to confirm the outcome diagnosis. Providers will be asked to send all available medical information occurring during the period of interest

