(surrounding the service date of the relevant claim). This information will include, but is not limited to:

- Labor and delivery records
- Office visit notes
- History and physical exam reports
- Laboratory reports
- Diagnostic imaging reports
- Hospital discharge summaries
- Surgical reports
- Histology/pathology reports
- Consultation/specialist notes

For each potential case, medical records will be sought if the patient is eligible for medical record retrieval. Approximately 50% of patients in the ORD are eligible for medical record retrieval. Patients who are ineligible for medial record retrieval include those from health plans that contract for administrative services only; access to medical records is not allowed for patients enrolled in these plans. For each eligible case, 1 medical record will be requested from 1 provider. Of those that are requested, approximately 70% to 85% of the medical records are expected to be successfully obtained (Johannes et al. 2007, Seeger et al. 2006). Therefore, the overall proportion of the ORD available for medical record validation is approximately 35 to 42.5%. Optum will seek up to 550 medical records.

Two clinical consultants with expertise in the field of teratology will be identified for the adjudication of MCMs, and 2 clinical consultants in the field of obstetrics will be identified for the adjudication of all other outcomes. Each pair of clinicians (blinded to study drug exposure) will review the clinical data for each potential case and adjudicate the outcomes. Each record will be adjudicated by 2 clinicians independent of one another, and consensus will be sought for discrepancies in adjudication results between the clinicians. Optum will work with the clinicians to arrive at consensus adjudications, and the Optum epidemiologist on the project will arbitrate the process. Optum will work with outside vendors as needed to procure the medical records and conduct the outcome adjudication.

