9.7.2.2. Descriptive analyses

For the descriptive analyses, the number of observations, mean, standard deviation, median, interquartile range, and range will be presented for continuous variables, and the number and percentage of patients in each category will be presented for categorical variables. In addition to all characteristics reported in the interim reports, the study cohorts will be described according to the covariates listed in Section 9.3.3. Characteristics will be reported separately

for those with and without COVID-19 diagnoses prior to cohort medication exposure, as well as by hospitalization status at the time of the start of the COVID-19 episode associated with treatment (if applicable).

Crude prevalence estimates and corresponding 95% CIs for pregnancy outcomes, and separately for infant outcomes, will be calculated using robust Poisson regression models, with the denominator for the pregnancy outcomes being the number of pregnancies from which the cases arose, the denominator for the infant outcomes being the number of linked livebirths, and the numerator being the number of cases, as described in Table 4. Logbinomial regression models will be included as sensitivity analyses.

Table 4. Statistical Analyses of Study Outcomes

Outcome	Measure of Frequency	Measure of Association (Regression Model)	Timing of Outcome Ascertainment	Unit of Analysis
SA	Prevalence	Prevalence ratio (Poisson)	Before Week 20 of pregnancy	Pregnancy
Induced termination	Prevalence	Prevalence ratio (Poisson)	Before Week 20 of pregnancy	Pregnancy
Stillbirth	Prevalence	Prevalence ratio (Poisson)	At or after Week 20 of pregnancy	Pregnancy
Livebirth	Prevalence	Prevalence ratio (Poisson)	At end of pregnancy	Pregnancy
MCM	Prevalence	Prevalence ratio (Poisson)	At birth or during infant follow-up	Linked livebirths
SGA	Prevalence	Prevalence ratio (Poisson)	At birth or during infant follow-up	Linked livebirths
Preterm birth	Prevalence	Prevalence ratio (Poisson)	At birth or during infant follow-up	Linked livebirths
Postnatal growth deficiency	Prevalence	Prevalence ratio (Poisson)	At birth or during infant follow-up	Linked livebirths
Infant developmental delay	Prevalence	Prevalence ratio (Poisson)	At birth or during infant follow-up	Linked livebirths

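### The primary comparative MCM analysis counts only chart-confirmed cases over all linked livebirths although charts reach 35 to 42.5% of patients, so MCM prevalence is understated and power for RR 2.0 is about 40 to 46%, not 80%

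*Protocol*

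**What the plan says.** **Outcome.** Protocol Section 9.1: "The primary outcome is MCM, which will be confirmed via medical record review". Section 9.3.1 puts MCM among the outcomes adjudicated from records: "Potential cases of MCM, induced termination, SGA, preterm birth, postnatal growth deficiency" and infant developmental delay, plus a sample of livebirths.

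**Numerator.** Section 9.7.2.3: "the primary comparative analyses in the final report will only include outcomes that have been confirmed via medical record review". The sentence goes on to admit outcomes found by published validated algorithms. Section 9.3.1.3 proposes these only for spontaneous abortion and stillbirth.

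**Denominator.** Section 9.7.2.2 has "the denominator for the infant outcomes being the number of linked livebirths". Table 4 gives linked livebirths as the unit of analysis for MCM, and Section 9.7.2.3 points to Table 4 for each outcome.

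**Chart reach.** Section 9.3.1.3: "Approximately 50% of patients in the ORD are eligible for medical record retrieval". Of the records requested, 70 to 85% are expected to arrive, so "the overall proportion of the ORD available for medical record validation is approximately 35 to 42.5" per cent.

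**Sample size.** Section 9.5 and Table 2 require 572 exposed livebirths, or 938 first-trimester exposed pregnancies, for MCM at RR 2.0 with 80% power. Comparative analyses go ahead for an outcome once its RR 2.0 minimum is reached. The only divisor applied is 0.61, for an observed outcome that is a livebirth.

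**The concern.** These statements do not fit together. A malformed infant whose chart is out of reach, because the plan is ineligible or the request fails, cannot enter the numerator but stays in the denominator as a non-case. Nothing in the protocol restricts the denominator to infants with reachable records or scales the confirmed cases up. Section 9.3.1.3 defends chart confirmation as highly sensitive because records may be sought for every potential outcome. The same section then says that about half the patients are ineligible.

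Three things are at stake.

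- Confirmed MCM prevalence would be well below the 3% background figure in Section 9.5. It would also not be comparable with spontaneous abortion and stillbirth, which are counted by algorithm without needing a chart.
- The 938 minimum opens the comparative analysis, and Section 9.7.1 allows accrual to be shortened once numbers suffice. A comparison with less than 50% power could start on the belief that it has 80%.
- In a safety study, a null result from such a comparison may be read as reassurance.

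**Working it through.** **Inputs (Protocol).** Eligibility 50% and retrieval 70 to 85% (Section 9.3.1.3). Comparator MCM prevalence 3%, RR 2.0, alpha 0.05, power 0.80, ratio 1:2 (Section 9.5). Two-sided likelihood ratio chi-square test (Table 2 footnote). Livebirth divisor 0.61.

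**1. Chart reach f.** 0.50 × 0.70 = 0.35 and 0.50 × 0.85 = 0.425. This reproduces the stated range.

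**2. The plan's sample size.** With h(p) = p ln p + (1 − p) ln(1 − p), group shares w1 and w2, and p̄ = w1·p1 + w2·p2:

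- δ = √{2[w1·h(p1) + w2·h(p2) − h(p̄)]}
- power ≈ Φ(δ√N − 1.96)

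For 6% vs 3%:

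| Exposed : comparator | δ | N | δ√N | Power |
|---|---|---|---|---|
| 572 : 1,144 (as labelled) | 0.07015 | 1,716 | 2.906 | 83% |
| 1,144 : 572 (reversed) | 0.06767 | 1,716 | 2.803 | 80% |

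The stated 572 is the exact 80% solution only with the group weights reversed. As labelled, 532 exposed livebirths give 80%. That is a separate matter and makes little difference here. 572/0.61 = 937.7, which rounds up to 938 as stated.

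**3. Confirmed prevalence over all linked livebirths.** Multiply by f.

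- Comparator: 3% × 0.35 = 1.05%; 3% × 0.425 = 1.275%.
- Exposed at RR 2.0: 6% × 0.35 = 2.10%; 6% × 0.425 = 2.55%.
- Events per group at 572:1,144: 572 × 6% = 1,144 × 3% = 34.3 true cases, of which 12.0 (f = 0.35) to 14.6 (f = 0.425) are confirmed.

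**4. Power with confirmed cases only, 572:1,144.**

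| f | Prevalences | δ | δ√1,716 | Power |
|---|---|---|---|---|
| 0.35 | 2.10% vs 1.05% | 0.04091 | 1.695 | 40% |
| 0.425 | 2.55% vs 1.275% | 0.04516 | 1.871 | 46% |

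Simulation of the likelihood ratio test (100,000 runs) gives 39% and 47%, and a Pearson calculation gives 42% and 49%. At the sizes that give exactly 80% before the loss (532:1,064, or 1,144:572), power falls to 37 to 44%.

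**5. Size needed for 80% power, 1:2.** Exposed livebirths: 1,564 (f = 0.35) or 1,284 (f = 0.425). In pregnancies: 1,564/0.61 ≈ 2,564 and 1,284/0.61 ≈ 2,105.

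**6. Restricting the denominator as well.** With both numerator and denominator limited to chart-reachable infants, prevalence returns to 3% and 6%, but power is still 40 to 47%. Restriction removes the downward bias and does not recover the lost information.

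**7. The ratio.** With equal f, (6% × f)/(3% × f) = 2.0, so it is unbiased. As an assumption for illustration, let reach be 35% in one cohort and 42.5% in the other. A true RR of 2.0 then reads as 2 × 0.35/0.425 = 1.65 or 2 × 0.425/0.35 = 2.43.

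**The case against.** **The confirmed-only rule is written for the comparative analyses.** These belong to secondary objective 2. The primary objective is the per-cohort risk, and Section 9.7.2.2 describes its numerator simply as the cases. A reader might infer that the primary-objective risk is, as written, understated by more than half. The documents do not say that. It follows only if the chart confirmation in Section 9.1 also defines those cases. That reading is plausible but unstated, and the protocol should settle it.

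**The ratio survives.** A reader might infer that the relative comparison is biased. With chart reach equal across cohorts it is not, and nothing in the protocol says that reach differs. The comparison loses precision. This point stands.

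**The plan has mitigations.** Claims-based results are presented alongside (Section 9.7.2.3). The final report gives identified, eligible, retrieved and confirmed counts, the PPV, and the characteristics of record-eligible and ineligible pregnancies (Section 9.7.2). Sensitivity analyses for missing records are planned (Section 9.7.3), and Section 9.3.1.3 leaves room for algorithms for further outcomes. A careful reader could rescale. But none of this changes the primary comparative estimate, the stated power or the 938 condition. Section 9.5 notes that incomplete retrieval could change the final sample size, yet applies no factor for it.

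**The SAP may resolve it.** Methods detail can sit there. However, the protocol itself fixes the numerator, the denominator and the sample size, and Section 9.7 requires major changes to primary endpoint definitions or their analyses to go into an amendment.

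**Two further inferences go too far.**

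- "Optum will seek up to 550 medical records" might be read as contradicting review of every potential case. Whether the cap binds depends on final accrual, on overlap between outcomes in the same infant, and on whether the 200 livebirth charts fall within the 550. The documents fix none of these.
- For the livebirth sample, "This conservative sample size is sufficient to exclude from the 95% confidence interval (CI) a PPV <80% if the true PPV is 85" per cent is met with 200 charts in hand: 0.85 − 1.96√(0.85 × 0.15/200) = 80.05%. If 200 eligible charts are requested, 140 to 170 arrive, and the same Wald limit is 79.1 to 79.6%. That is a small shortfall and worth no more than a note.

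**Conclusion.** The point holds for the primary comparative MCM analysis. By construction, the confirmed prevalence is 35 to 42.5% of the true one, so 3% reads as about 1.05 to 1.28%. Power for RR 2.0 at the Table 2 size is about 40 to 46%, against a stated 80%. The stated minimum of 572 livebirths or 938 pregnancies would have to be about 1,284 to 1,564 livebirths, or 2,105 to 2,564 pregnancies. The same numerator and denominator mismatch affects every other infant outcome that is to be chart-confirmed.

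These figures assume that the claims screen finds nearly all true MCMs, that chart reach is unrelated to MCM status, that the stated eligibility and retrieval rates hold, and that no validated MCM algorithm is adopted before the final analysis. The conclusion concerns the absolute prevalence in these analyses and their power. It extends to the primary-objective risk only if confirmation also defines the cases there.

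**What to change.** 1. **Align numerator and denominator** for every chart-confirmed outcome. Choose one of the following as primary and report the other as sensitivity:
   - Restrict both to record-eligible pregnancies, with inverse weighting for non-retrieval.
   - Keep all linked livebirths and correct the claims-identified cases with a chart-derived PPV, carrying its uncertainty through by bootstrap or multiple imputation. Pool the PPV across cohorts where counts are small. At the protocol's 670 Cohort 2 pregnancies, only 670 × 0.61 × 3% ≈ 12 MCMs are expected, too few for a stable cohort-specific PPV.
2. **State in Section 9.7.2.2** whether the cases in the per-cohort MCM risk are chart-confirmed or claims-identified.
3. **Restate the power, the Table 2 minimum and the Section 9.5 condition** for comparative analyses to reflect expected chart reach under the chosen method. This does not require more enrolment; it requires that the stated power be the one the analysis has.

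**Cost.** Protocol and SAP wording, modest extra analysis, and no additional charts. Intervals will be wider, and the result will rest on an assumption that PPV or retrieval carries over to record-ineligible plans. The planned description of eligible and ineligible pregnancies helps to judge that assumption.

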9.7.3. Missing data

This study is based on an analysis of automated medical and prescription claims, supplemented by information abstracted from medical records. Using the standard approach in claims data analyses, the presence of a medication or disease claim will be assumed to indicate use of that medication or the presence of that disease and conversely, the absence of a medication or disease claim will indicate the absence of use of that medication or a diagnosis of that disease. Outcome data may be missing due to health plan disenrollment, or non-linked infants and missing or limited medical records. Sensitivity analyses are planned to assess the degree of bias potentially introduced by non-linkage of infants and missing or non-informative medical records. All retrieved medical records will be reviewed for mention of MCMs, as pregnancies that result in non-livebirths may not always capture MCMs in medical claims.

9.7.4. Additional analyses

9.7.4.1. Sensitivity analyses to account for exposure misclassification

As the association between maternal exposure and occurrence of pregnancy and infant outcomes may differ by timing of the exposure relative to fetal development, additional analyses will be conducted to assess the risk of MCMs by second and third trimester exposure (in addition to the primary analysis of first trimester and full pregnancy exposure windows). Additional alternative exposure windows (eg, a combined first and second trimester window of exposure, or weeks of gestation relating to organogenesis) may be considered, as sample size allows.

